Assignment to study arms is implemented at the level of the vaccination event, with all vaccination events scheduled during a phase assigned to the corresponding arm. T_1 , the beginning of Phase 1, denotes the time of participants' enrollment into the control arm. At time T_2 , the beginning of Phase 2, all participants are rolled over to the arm with reminders; at time T_3 , the beginning of Phase 3, all participants are rolled over to the arm with reminders combined with incentives. While T_2 and T_3 denote fixed points in calendar time, variation in delivery dates across participants results in between- and within-individual variation in the assignment of vaccination events across the three arms. **Table 2** shows all possible combinations of vaccination event assignments to study arms at the level of the participant. With dates of birth exogenously determining children's vaccination schedules, shifts in T_2 and T_3 directly affect the number of vaccination events that may be observed in each study phase. Based on the distributions of expected delivery and vaccination due dates, T_2 and T_3 are chosen such that the expected number of vaccination events is approximately equal across the three arms. With T_2 and T_3 being random in relation to mothers' delivery dates, and thus children's vaccination schedules, the assignment of vaccination events across arms may be considered quasi-random. Loss to follow-up and other reasons for non-delivery of vaccination reminders result in exposure indistinguishable from the control condition.

The assignment to study arms based on scheduled vaccination dates, and the simultaneous transition of all participants between study arms, address concerns that the individual randomization into, and co-existence of, incentive and non-incentive arms are not considered viable within closely-knit communities. While cluster randomization was considered as an alternative approach, the heterogeneity of clusters suggests that this approach would confound the effects of settings with the effects of reminders and incentives.

Study setting

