timing of the next scheduled vaccination, may themselves function as an intervention. Fifth, temporal changes that coincide with the points of transition between study arms could influence results. Finally, while the primary focus of the study is on demand-side barriers to timely vaccinations, participating health facilities may encounter vaccine stock outs and power outages, resulting in vaccination activities being deferred until vaccine stocks are received or power is restored. We plan to monitor these events along with mHealth system and mobile network metrics (e.g., message transmission errors, calls dropped) during the study period. By characterizing, and if possible, addressing the limitations of our study, we will provide critical information for the feasibility of scaling up reminders and/or incentives to the regional or national levels in low-resource settings such as Tanzania.

With the continuing diffusion of mobile phones and the ongoing development of mHealth technologies, adaptive programming in the form of dynamic reminder systems and variable incentive structures has become a feasible reality even in low-resource settings. Our study sheds light on the demand-side barriers to vaccinations and the synergistic potential of combining mHealth reminders and incentives for improving vaccination coverage and timeliness. The results have implications for the design and potential efficacy of other subsidy or incentive programs aimed at improving health and health seeking behaviors.

References

1. World Health Organization. *Immunization coverage*. 2016 September 2016 [cited 2016 November 07]; Available from: <http://www.who.int/mediacentre/factsheets/fs378/en/>.
2. World Health Organization, *Global Vaccine Action Plan 2011-2020*. 2013, World Health Organization: Geneva, Switzerland.
3. Global Immunization Division, Centers of Disease Control and Prevention, and World Health Organization, *Epidemiology of the unimmunized child: Findings from the peer-reviewed published literature, 1999-2009*. 2009.
4. World Health Organization. *Immunization, Vaccines and Biologicals*. 2017 [cited 2017 October 26]; Available from: <http://www.who.int/immunization/en/>.
5. The DHS Program. *Demographic and Health Survey, and Malaria Indicator Survey, Tanzania*. 2015-16 [cited 2017 June 09]; Available from: <https://dhsprogram.com/pubs/pdf/FR321/FR321.pdf>.

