mHealth-Assisted Conditional Cash Transfers to Improve Timeliness of Vaccinations (MINT)

ClinicalTrials.gov ID NCT03252288

Statistical analysis

For each participant, outcomes are observed at three time points (corresponding to timely vaccinations at 6, 10 and 14 weeks, respectively). The probability of timely vaccinations and its association with reminders and incentives will be analyzed in a bivariable analysis and using a random effects logistic regression model. The outcome variable is 1 if the vaccination was received on-time, and 0 if early, delayed, or not received at all. The primary covariates of interest are indicator variables for the receipt of reminders only (“*reminder*”) and the receipt of reminders with an incentive offer (“*reminder+incentive*”). For arm 1 the value of both covariates is 0 for all three time points. For outcomes in arm 2, the value for *reminder* (and for arm 3 the value for *reminder+incentive*) is 1 if the mHealth system confirmed delivery of the reminder, and 0 for all other observations. Additional covariates (e.g. mother’s education, rural vs. urban residence, recruitment from health facilities vs. the community) will control for differences in participant characteristics between study arms and their association with vaccination timeliness. Interactions of *reminder* and *reminder+incentive* with these covariates describe systematic variation in the effects of reminders and incentives on vaccination timeliness. Models will control for the number of phone-based contacts prior to or within the timeliness window for any given vaccination, and standard errors will be adjusted to account for clustering at the level of the health facility catchment area.

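### The arms are consecutive calendar periods with no concurrent control, so birth-date variation does not protect against a gradual time trend, and no calendar-time analysis is prespecified

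*Protocol*

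**What the plan says.** The protocol section on assignment to study arms makes the vaccination event the unit, with "all vaccination events scheduled during a phase assigned to the corresponding arm". It states that "T_2 and T_3 denote fixed points in calendar time" and describes a "simultaneous transition of all participants between study arms". On how the dates are set, it says that "T_2 and T_3 are chosen such that the expected number of vaccination events is approximately equal across the three arms". The next sentence argues from "With T_2 and T_3 being random in relation to mothers' delivery dates" that "the assignment of vaccination events across arms may be considered quasi-random". The Study design section accordingly labels the trial quasi-randomised.

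The Statistical analysis section of the protocol and the SAP give the same regression model: indicators for confirmed delivery of a reminder or of a reminder with an incentive offer, example participant covariates, interactions, the number of phone contacts, and standard errors clustered by catchment area. The example covariates "will control for differences in participant characteristics between study arms". Calendar time and season are not named in either document.

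The fifth limitation in the protocol's Discussion is that "temporal changes that coincide with the points of transition between study arms could influence results". No analysis is attached to it.

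**The concern.** Under this rule the assigned arm is a fixed function of the scheduled date. Everything due before T_2 is control, everything due after T_3 is reminder plus incentive, and no date has two assigned arms. If birth dates are exogenous, chance decides which children contribute to which phase. That helps to balance children. It does nothing to balance calendar time, whichever way T_2 and T_3 are picked, and they are picked from the expected due dates rather than drawn at random.

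The acknowledged limitation is narrower than the threat. A smooth trend in timeliness has no feature at T_2 or T_3, yet it moves the phase means apart. With no time term in the model, that movement goes into the two exposure coefficients. The aim is efficacy against standard of care, so what is at stake is whether a difference between periods can be read as an effect of reminders or incentives. An upward trend would add to both effects, more so for the later arm. A downward trend, for example a fading effect of enrolment, would hide benefit.

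**Working it through.** **Inputs from the protocol (Statistical power).** Up to 1,200 events, equal arms, 10% attrition, clusters of 10 women with intra-cluster correlation 0.02, 3 observations per child with correlation 0.2, control rate 65%, effects of 10 and 15 points, two-sided alpha 0.05, stated power 72% and 98%.

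**Inputs assumed, because the documents give no phase or recruitment lengths.** Uniform enrolment over 4 to 24 weeks at 28 to 39 weeks of gestation; birth at the expected date with SD 1.7 weeks; events due 6, 10 and 14 weeks after birth; T_2 and T_3 at the terciles of due dates; a linear trend on the probability scale.

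**Step 1: the plan's own power.** Events per arm are 1,200 × 0.9 / 3 = 360. The documents do not state their formula. I used the normal approximation for two proportions.
- Child design effect 1 + 2 × 0.2 = 1.4, times (1 − 0.02) because each catchment area passes through all arms, gives 1.372. Then 360 / 1.372 = 262 effective events, with power 70.6% and 97.2%, within 2 points of the stated figures.
- Multiplying in the usual cluster effect, 1 + 9 × 0.02 = 1.18, gives 1.652 and 218 effective events, with 62.5% and 94.2%. That does not reproduce the plan.
- About 270 effective events per arm gives 72% and 98%. I use 270 below.

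**Step 2: bias with full delivery.** Write g2 and g3 for the gaps in mean due date between control and arms 2 and 3, and s for the trend per week. With no true effect, the coefficients equal s × g2 and s × g3. The simulated calendar gives g2 = 5.5 to 9.5 weeks and g3 = 11.0 to 18.9 weeks. For 1 point per 4 weeks, s = 0.25:
- reminder: 0.25 × 5.5 = 1.4 to 0.25 × 9.5 = 2.4 points;
- reminder+incentive: 0.25 × 11.0 = 2.8 to 0.25 × 18.9 = 4.7 points.

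Adding terms for the 6-, 10- and 14-week visit leaves 1.2 to 2.3 and 2.5 to 4.6 points, so visit terms do not remove it.

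**Step 3: bias under the planned coding.** Undelivered events in Phases 2 and 3 join the reference group. If a fraction u is undelivered at random, the reference mean date moves later by u(g2 + g3) / (1 + 2u).
- u = 0.1, short calendar: 0.1 × 16.5 / 1.2 = 1.375 weeks, so 0.25 × 4.125 = 1.0 and 0.25 × 9.625 = 2.4 points.
- u = 0.1, long calendar: 0.1 × 28.4 / 1.2 = 2.367 weeks, so 0.25 × 7.133 = 1.8 and 0.25 × 16.533 = 4.1 points.
- u = 0.3, same formula: 0.6 to 1.0 and 2.0 to 3.4 points.

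**Step 4: false positives.** A second calendar, with births uniform over an assumed 13 weeks, spans 13 + 8 = 21 weeks with gaps of 5.6 and 11.1 weeks (27% and 53% of the span). The table assumes full delivery and 218 to 271 effective events per arm; the nominal rate is 5%.

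| Drift over the span | Spurious effect, reminder / reminder+incentive | False-positive rate, reminder / reminder+incentive |
|---|---|---|
| 5 points (about 1 per 4 weeks) | 1.3 / 2.7 points | 6% / 9–10% |
| 10 points | 2.7 / 5.3 points | 9–10% / 22–26% |

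**Step 5: cost of a linear due-date term, full delivery.** On the recruitment calendar, standard errors rise about 1.5 times (reminder) and 2.3 to 2.5 times (reminder+incentive). Power was worked out on the birth-window calendar, for windows of up to 26 weeks, where inflation is similar or slightly higher:
- reminder: variance up 2.26 to 2.50 times; 270 / 2.26 = 119 and 270 / 2.50 = 108 effective events; power 39% to 36%;
- reminder+incentive: variance up 6.03 to 7.00 times; 270 / 6.03 = 45 and 270 / 7.00 = 39 effective events; power 35% to 31%.

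These steps use a linear probability model without the child random effect or the phone-contact covariate.

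**The case against.** The sequential design was a reasoned choice. The protocol explains that co-existing incentive and non-incentive arms were judged unworkable in close communities, and that cluster randomisation was rejected because the clusters differ too much. That stands, and nothing here asks for a redesign.

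Temporal change is already listed as a limitation. That stands in part: the threat is recognised, but only at the transition points and without an analysis.

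The covariates are introduced as examples, so due date could still be added. This also stands. The fair statement is that a time term is not prespecified; the documents do not exclude one.

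Confirmed-delivery coding leaves some later events in the reference group, which gives some overlap in time. Step 3 shows that this shrinks the bias without removing it. The protocol attributes non-delivery to loss to follow-up and other reasons, so these events are not a sound concurrent control.

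The documents report no trend. One point per 4 weeks is 52 / 4 = 13 points a year, which is an illustration and not an estimate.

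Finally, the remedy is weak. A linear term costs much precision, and because each phase occurs once it cannot tell a seasonal or curved pattern from the arms. This stands, and it is why the term belongs in a sensitivity analysis and why the wording changes matter as much as the model.

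**Conclusion.** The point holds. Quasi-random describes which child's event falls in which phase; it does not describe the relation of phase to time. A monotone trend in either direction biases both coefficients, and the plan prespecifies nothing that would show it. At the illustrative drift the shift is modest for reminders and larger for reminders with incentives. Its size depends on the assumed recruitment period, the linear trend and the delivery rate, none of which the documents supply.

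A reader might infer more than this, without support:
- That any drift or season biases the result. A fluctuation with equal phase averages would not.
- That the bias must favour the interventions and imitate a dose-response. A downward trend would mask benefit. The roughly twofold ratio between the two shifts holds only with full delivery; with 30% undelivered it is about 3.3.
- That drift could account for the whole of the planned effects. No figure in the documents supports a trend steep enough for that.

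**What to change.** 1. **Protocol, Study design and Assignment to study arms.** Describe the arms as consecutive calendar periods without concurrent controls. Say that birth-date variation makes the allocation of children to phases arbitrary but does not separate phase from time. Keep the existing feasibility rationale.
2. **Protocol, Discussion.** Widen the fifth limitation to gradual trends and season.
3. **Protocol and SAP, Statistical analysis.** Prespecify a sensitivity analysis that adds each event's scheduled due date, linear in weeks, to the main model. Use the same due date that places the event in its phase. Report both exposure coefficients with confidence intervals, with and without the term. State that the term cannot separate season or a non-linear trend from arm, because each phase occurs once.

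The main model stays primary. Attribution should not hang on the sign of the adjusted coefficient: with no true effect, an unbiased estimate is positive half the time.

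The cost is wording plus one model on due dates that the scheduling system already holds. The downside is the imprecision in step 5, so wide intervals from the sensitivity model should be read as showing how closely arm and time are aligned, not as evidence of no effect.

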Women providing informed consent are enrolled in the study. At the time of enrollment, a baseline survey is conducted with all participants to assess socio-demographic characteristics, mobile phone ownership and use, reproductive history, EDD for the current pregnancy, and vaccination knowledge, history of vaccinations in a prior child, if applicable, and previously experienced or anticipated barriers to vaccinations. Mobile phone numbers are obtained for mothers and any authorized agents. Surveys are implemented electronically on tablet devices

and conducted by study staff at health facilities, participants' homes, or other mutually agreed-upon locations.

Toward the end of Phase 1, all women are contacted by phone to ascertain birth dates and outcomes, and information on past and scheduled vaccinations. The information is used to generate child-specific vaccination schedules. In Phases 2 and 3, reminder messages are sent to registered mobile phone numbers 1 week and 1 day prior to each scheduled vaccination, and, if no vaccination confirmation is received, 2 weeks after the vaccination due date. Uniquely numbered cards, given to participants at each completed or rescheduled vaccination, allow participants to report vaccination dates via the USSD system. When no vaccination report is received via the USSD system, SMS, or phone calls from participants, study staff contact the participant by phone to verify whether and when a vaccination was received, and ascertain the due date for the next vaccination, if applicable. Recorded vaccination dates are used to iteratively update vaccination schedules and to re-schedule reminders.

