For each participant, outcomes are observed at three time points (corresponding to timely vaccinations at 6, 10 and 14 weeks, respectively). The probability of timely vaccinations and its association with reminders and incentives will be analyzed using a random effects logistic regression model. The outcome variable is 1 if the vaccination was received on-time, and 0 if early, delayed, or not received at all. The primary covariates of interest are indicator variables for the receipt of reminders only (“*reminder*”) and the receipt of reminders with an incentive offer (“*reminder+incentive*”). For arm 1 the value of both covariates is 0 for all three time points. For outcomes in arm 2, the value for *reminder* (and for arm 3 the value for *reminder+incentive*) is 1 if the mHealth system confirmed delivery of the reminder, and 0 for all other observations. Additional covariates (e.g. mother’s education, rural vs. urban residence, recruitment from health facilities vs. the community) will control for differences in participant characteristics between study arms and their association with vaccination timeliness. Interactions of *reminder* and *reminder+incentive* with these covariates describe systematic variation in the effects of reminders and incentives on vaccination timeliness. Models will control for the number of phone-based contacts prior to or within the timeliness window for any given vaccination, and standard errors will be adjusted to account for clustering at the level of the health facility catchment area.

Statistical power

Across 400 participants we expect up to 1,200 data points on vaccination timeliness. Assuming (a) that these data points are distributed equally across the 3 study arms (standard of care; reminders only; reminders and incentive); (b) a 10% attrition rate; (c) equal cluster sizes of 10 women per health facility catchment area, with an intra-cluster correlation of 0.02; (d) 3 observations per child, with a within-child correlation of 0.2; (e) a baseline rate of vaccination timeliness of 65% in the control condition; and (f) a 10 (15) percentage point difference associated with reminders (reminders and incentives), the power ($\alpha=.05$, 2-tailed) to detect such difference is 72% (98%).

Dissemination

Results will be shared with stakeholders at the regional and national levels, presented at national and international conferences, and published in high impact academic journals.

Data sharing

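### Lost events are given control exposure and unknown outcomes have no code: keeping them and scoring them as failures would create a false effect of up to 16 points at the planned 10% loss

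*Protocol*

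**What the plan says.** Four parts of the plan bear on this.

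- **Lost events.** Protocol, Assignment to study arms and transitions between arms: "Loss to follow-up and other reasons for non-delivery of vaccination reminders result in exposure indistinguishable from the control condition".
- **Exposure.** Protocol and SAP, Statistical analysis: each indicator "is 1 if the mHealth system confirmed delivery of the reminder, and 0 for all other observations". An arm 2 or arm 3 event without confirmed delivery therefore has 0 on both indicators, the same as an arm 1 event.
- **Outcome.** Same sections: "The outcome variable is 1 if the vaccination was received on-time, and 0 if early, delayed, or not received at all". Neither document gives a code for an event whose vaccination status is not known, or any missing-data rule.
- **Sources of outcome data.** Protocol, Study activities: participants report by phone, and when no report arrives, "study staff contact the participant by phone to verify whether and when a vaccination was received". An in-person survey 12 months after enrollment also records dates from the vaccination card. Its stated purpose is comparison with the mHealth system's data. Neither document says which source defines the outcome.

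The Statistical power section starts from the statement "Across 400 participants we expect up to 1,200 data points on vaccination timeliness" and assumes "b) a 10% attrition rate".

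**The concern.** A woman who drops out of phone contact in phase 2 or 3 can fail to receive the reminder and also fail to report the vaccination. The first failure moves her event into the reference group. The second leaves the outcome unknown, and the plan does not say what then happens to the event. If it is treated as a vaccination that did not take place, failures to observe collect in the reference group and none enter the delivered-reminder groups. Both intervention contrasts would then look favourable even if reminders and incentives did nothing. An unstated data-handling choice would decide whether the primary contrast is unbiased on this count or carries a false effect as large as those the trial was designed to detect.

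**Working it through.** **The plan's own figure.** The only quantitative result in the plan is power of 72% for a 10-point difference and 98% for 15 points. Its inputs include "equal cluster sizes of 10 women per health facility catchment area, with an intra-cluster correlation of 0.02" and a within-child correlation of 0.2 over 3 observations. With 400 × 0.9 = 360 events per arm and a design effect of (1 + 9 × 0.02)(1 + 2 × 0.2) = 1.652, the effective number is 217.9 per arm and a two-sided test gives 62.5% and 94.2%. The plan does not state its formula. An additive design effect of 1 + 0.18 + 0.2 = 1.38 gives 70.4% and 97.2%, and comparisons within a child can lower the design effect. I do not call the stated power wrong, and nothing below depends on it.

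**Inputs from the Protocol, Statistical power.** Up to 1,200 events; "these data points are distributed equally across the 3 study arms", so 400 per arm; 65% on time in the control condition; 10% attrition; planned differences of 10 and 15 points.

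**Assumptions of mine.** No true effect, so 65% on time in every arm. Equal loss q in each arm. Every lost arm 2 or arm 3 event has no confirmed delivery. Loss rates other than 10%, and the share r of lost outcomes recovered from cards, are illustrative.

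**Step 1: lost events kept as control exposure and scored 0.**

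- Observed arm 1 events: 360, of which 0.65 × 360 = 234 are on time.
- Lost events joining the reference group: 40 + 40 + 40 = 120, none on time.
- Reference rate: 234/480 = 48.75%.
- Delivered-reminder rate in arm 2, and likewise arm 3: 234/360 = 65%.
- False difference: 16.25 points. Odds ratio: (0.65/0.35)/(0.4875/0.5125) = 1.95.

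**Step 2: general form.** With on-time probability p, the false difference is 3pq(1 − r)/(1 + 2q).

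| Loss q | r = 0 | r = 0.5 |
|---|---|---|
| 5% | 8.9 points | 4.4 points |
| 10% | 16.25 points | 8.1 points |
| 15% | 22.5 points | 11.3 points |
| 20% | 27.9 points | 13.9 points |

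**Step 3: other ways of handling the same 10% loss.**

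- Arm 1 losses excluded, arm 2 and arm 3 losses moved in: 234/440 = 53.2%, a false difference of 11.8 points.
- Lost events set to missing: 65% against 65%, difference 0.
- Lost events scored 0 but kept in the assigned arm: 0.65 × 0.90 = 58.5% in every arm, difference 0.

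The artefact therefore needs both steps together: the move into the reference group and the score of 0.

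**Step 4: does a random intercept remove it?** These percentages correspond to the bivariable analysis that the SAP names. For the regression, I rely on a simulation of a random-intercept logistic model under no true effect with 10% loss (120 runs per scenario, births assumed uniform over 12 weeks, within-child correlation about 0.15). With lost events scored 0 in the reference group, the median odds ratio for reminders was 1.74 when whole women were lost (null rejected in 80% of runs) and 2.09 when single events were lost (100%). With lost events dropped it was 0.99 to 1.03 (6% to 7% rejected). With zeros kept in the assigned arm it was 0.98 to 1.00. This shows that a random intercept does not by itself remove the artefact; it is not a replica of the full planned model.

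**The case against.** The strongest reply is that no sentence scores an unobserved vaccination as 0. The outcome rule lists states of receipt, and unknown is not one of them. The sentence on loss to follow-up describes what a woman experienced, not who is analysed. It can be read consistently with the attrition allowance: an event without a delivered reminder counts as unexposed when its outcome is known, and drops out when it is not. On that reading the false difference is 0. This stands. A reader might infer that the plan manufactures a reminder effect, or that its assignment and power sections contradict each other. The documents support neither; they leave the choice open.

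The link between non-delivery and an unknown outcome is also loose. The USSD dialog can be reached from any mobile phone, agents' numbers are held as well as mothers', and one card seen at the in-person survey can supply all three outcomes. So 16 points is a worst case at 10% loss. What does not stand is that the cards settle the matter: they are not named as the outcome source, and nothing is said about a woman without one.

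Two further inferences go too far. One is that an analysis by phase would be biased against the later arms because loss accumulates. That needs loss rates rising by phase, which the documents do not give, and an exposure coding that they do not plan. The other is that a child's death before the due date is scored as an untimely vaccination. No passage says so; the plan is silent.

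**Conclusion.** The concern holds in conditional form. The documents establish that lost events carry control exposure, that undelivered events join the reference group, that the outcome has no unknown state, and that no outcome source takes precedence. They do not establish how an unknown outcome is scored. That open choice moves the primary contrast, under no true effect and at the plan's own 10% loss, from 0 (events dropped, or scored 0 in the assigned arm with equal loss) through about 8 points (half recovered from cards) and about 12 (arm 1 losses excluded) to 16.25, against planned differences of 10 and 15. The nonzero figures assume that lost arm 2 and arm 3 events lack confirmed delivery and that unrecovered ones are scored 0.

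Setting unknowns to missing cures this artefact only. Women whose reminders are not delivered may differ in timeliness for other reasons, and coding exposure by delivery leaves that selection in place. It is a separate problem, and it is one reason why the fix below also keeps events in their assigned phase.

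**What to change.** Amend the Statistical analysis section of both documents to say:

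1. The outcome is taken from the end-line vaccination card where available, and otherwise from a report or contact made after the timeliness window closed.
2. An event is scored 0 only when non-receipt, or a date outside the window, is established. Every other event without a known outcome is missing.
3. Events where the child died before the due date are excluded.
4. In the primary analysis every event stays in its assigned phase. Lost or undelivered events are not recoded as control. Exposure by confirmed delivery can remain as a secondary analysis.
5. The number of unknown events is reported by phase, and a sensitivity analysis scores unknowns as 0 within the assigned phase.

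The cost is SAP wording and one extra model. Slightly fewer events are analysed, which the 10% attrition allowance already anticipates. Analysis by assigned phase dilutes a true effect where reminders do not arrive: if 10% of arm 2 events with known outcomes had no delivery (an assumption), a 10-point effect would appear as 0.9 × 10 = 9 points. Complete-case analysis also assumes that missingness is not informative within phase. That could fail, for example because only phase 3 pays for timely vaccination on the strength of participants' reports. The counts by phase and the sensitivity analysis probe this but do not remove it.
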